8.3. KEY SECONDARY EFFICACY ENDPOINTS AND ANALYSES

8.3.1. Clinical Global Impression - Improvement (CGI-I) Rating, as assessed by the Principal Investigator

The Principal Investigator will rate their global impression of the subject's condition at each clinic visit after randomization: at the end of the Titration period Visit 6 (Day 15), during the Maintenance period at Visit 8 (Day 43) and Visit 10 (Day 71), and at Visit 12 (End of Study / Early Termination).

The CGI-I scale measures the change in the subject's clinical status from a specific point in time, i.e., the Baseline Period. The CGI-I rating scale permits a global evaluation of the subject's improvement over time. The severity of a subject's condition is rated on a 7-point scale ranging from 1 (very much improved) to 7 (very much worse) as follows:

1=very much improved 2=much improved 3=minimally improved 4= no change 5=minimally worse 6=much worse 7=very much worse

The mean (SD) CGI-I score, and the number and percentage of subjects who showed improvement (i.e., had a score of 3 or lower), and the number and percentage who did not improve (i.e., had a score of 4 or higher) will be presented for each for each treatment group at each assessment time point. Each assessment time point will include a comparison between each active treatment and the placebo group using the Cochran-Mantel-Haenszel test (CMH) stratified by weight strata, and a frequency distribution of the number and percentage of subjects in each category in the scale. A graphic showing the percentage of respondents in each category will be presented.

The number and percentage of subjects who showed clinically meaningful improvement (i.e., had a score of 2 or lower), and the number and percentage who did not have clinically meaningful improvement (i.e., had a score of 3 or higher) will be presented for each treatment group at each assessment time point as an exploratory analysis.

Individual subject CGI data will be listed.

8.4. ADDITIONAL EFFICACY ENDPOINTS AND ANALYSES

8.4.1. Countable Motor Seizures Definition and Analysis

The change in the frequency of countable motor seizures per 28 days between the Baseline and T+M periods will be calculated using the same methodology described for the primary endpoint. Countable motor seizures include:

- generalized tonic-clonic seizures [GTC]
- secondarily generalized tonic-clonic [SGTC]
- tonic seizures [TS]
- atonic seizures [AS]
- tonic/atonic seizures [TA]
- clonic seizures [CS]
- hemiclonic seizures [HS]
- focal seizures [FS] with clear observable motor signs

3 authorization A change in the frequency of countable motor seizures per 28 days between the Baseline and M period will also be calculated.

The same non-parametric and parametric ANCOVA models described for the primary endpoint will be used for the analyses of countable motor seizures (change in the frequency between Baseline and T+M periods). The mITT population will be used for this analysis. The difference between 0.8 mg/kg/day and placebo in the change between Baseline and T+M is a secondary endpoint. The analyses will be repeated for the change in frequency between the Baseline and M periods. The analysis of the change between Baseline and the M period is one of the additional secondary endpoints.

The number and percentage of subjects who had a worsening, 0% reduction, ≥25% reduction, ≥50% reduction, ≥75% reduction, and 100% reduction in the frequency of countable motor seizures between Baseline and T+M and between Baseline and M will be summarized by treatment group and overall. These analyses are part of the additional secondary endpoints.

Additional Seizure Counts 8.4.2.

The other efficacy endpoints of change in the frequency per 28 days between Baseline and T+M peropd and between Baseline and M period of:

- All Typical Drop Seizures (i.e., GTC, SGTC, TS, AS, TA regardless of ESC confirmed as drop or not)
- All Countable Non-Motor Seizures
- All Countable Seizures

Each of these endpoints will be calculated using the same method as the primary endpoint. The same non-parametric ANCOVA, parametric ANCOVA, and logistic regressions used for the primary efficacy endpoint will be used. The mITT population and PP populations will be used for these analyses.

Refer to Appendix 1 for the seizure types that are included in each of these endpoints.

8.4.3. Seizure-Free Days

Seizure free days will be taken from the parent/caregiver diary data.

A seizure free day with no seizures leading to drops will be defined as a day for which diary data are available and with no ESC-defined drop seizures. A day without countable motor seizures will be defined as a day for which diary data are available and with no countable motor seizures. The total number of countable seizure-free days and drop seizure-free days will be summed for the entire T+M period and similarly for the baseline period.

Seizure-free days per 28 days at baseline = (number of seizure free days during baseline)*28/ (number of days during baseline with non-missing diary data)

Seizure-free days per 28 days during T+M Period = (number of seizure free days during T+M Period)*28/ (number of days during T+M Period with non-missing diary data)

Statistical comparison of treatment groups and placebo on the number of seizure free days per 28 days and drop seizure-free days per 28 days during T+M using the baseline as covariate will be done with a similar non-parametric ANCOVA model as described for the primary analysis.

8.4.4. Duration of the Longest Interval between Seizures Resulting in Drops

The duration of longest interval between seizures resulting in drops (in days) will be analyzed using nonparametric methods.

For each subject, the duration of the longest interval between seizures resulting in drops (i.e., ESC confirmed) will be calculated over the entire T+M period. This will be derived as the maximum of the number of consecutive days between seizures resulting in drops. The length of the intervals between seizures resulting in drops will be calculated as below, after which the duration of the longest interval between convulsive seizures will be derived.

If a subject has a missing diary day within an otherwise seizure-free interval, that day is counted towards the duration of the seizure free interval. However, if a subject has two consecutive days of missing diary data, the current seizure-free interval will end on the first date of missing diary data, and a new one begun on the next date that diary data are available and no seizure occurs. [In that case, for purpose of calculation of this variable, all intervening days, after the 2nd day, with missing diary data, will be assumed to have a seizure with drops occurrence, until the first available date with non-missing diary data.]

Let Date0 (=Day1) be the first day of treatment. If a seizure resulting in a drop occurs on five days having dates as Date1, Date2, Date3, Date4, and Date5, where Date5>Date4>Date3>Date2>Date1≥Date0, and let LDT = Last date of treatment in the maintenance period, where LDT ≥ Date5, then the time interval between convulsive seizures will be calculated as follows:

Version 2.0

Syneos Health #1009529A

I1=Date2 - Date1

12=Date3 - Date2

13=Date4 - Date3,

14=Date5 - Date4.

For completeness, we calculate the time to the first seizure as

10=Date1 - Date0,

and the time from the last seizure to end of treatment as

15 = LDT - Date5.

Here the duration of the longest interval =Maximum (10, 11, 12, 13, 14, 15).

If the subject does not experience a seizure during treatment, then the last available diary date will be used to compute the duration of the longest interval as follows:

The longest interval=last available diary date DateO

The median time of the longest interval between seizures resulting in drops (in days) will be presented. Additional summary statistics will be presented, including mean, minimum, maximum, and the 25th and 75th percentiles, 95% confidence intervals on the difference in medians between groups (Hodges-Lehman estimator).

The Wilcoxon rank sum test will be used to test for differences between each treatment arm and placebo, and the p-value from this test will be presented. A boxplot summarizing the duration of the longest interval between seizures will be provided.

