Part 1 consists of a 4-week baseline, 2-week titration, 12-week maintenance, and 2week taper or transition period. The 4-week Baseline Period consists of the establishment of initial eligibility during a screening visit to include an assessment of cardiac parameters (ECG and ECHO), followed by an observation period where subjects will be assessed for baseline seizure frequency based on recordings of daily seizure activity entered into a diary. Upon completion of the Baseline Period, subjects who qualify for the study are randomized (1:1:1) in a double-blind manner to receive 1 of 2 doses of ZX008 (0.2 mg/kg/day, 0.8 mg/kg/day; maximum dose: 30 mg/day [or 0.5] mg/kg/day, maximum 20 mg/day, for subjects taking concomitant STP]) or placebo. Randomization is stratified by weight (<37.5 kg, $\ge 37.5 \text{ kg}$) to ensure balance across treatment arms, and at least 25% of subjects will be in each weight group. All subjects are titrated to their blinded randomized dose over a 2-week Titration Period. Following titration, subjects continue treatment at their randomly assigned dose over a 12-week Maintenance Period. Total treatment time from the beginning of the Titration Period through the end of the Maintenance Period is 14 weeks. Subjects will have ECG and ECHO assessments at weeks 6 and 14 during the Maintenance Period. At the end of the Maintenance Period (or early discontinuation), all subjects undergo a blinded 2-week taper or transition period (Post-Dosing Follow-Up) depending on whether they exit the study or are enrolled in Part 2, the long-term open-label extension, respectively. Cardiac safety follow-up visits are performed after study drug discontinuation for early termination, or for those subjects who complete the study but do not enter the openlabel extension part. All subjects are required to have follow-ups at 3 and 6 months. Subjects enrolled in Germany, France and Netherlands will have an additional follow-up at 24 months. If there are any findings at a post-dose follow-up, a follow-up visit will be scheduled every 3 months until resolved or stabilized.

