6.6. GENERAL ASPECTS FOR STATISTICAL ANALYSIS

6.6.1. General Methods

All statistical analyses will be performed using SAS statistical software (Version 9.4 or later).

Part 1 summaries will be presented by treatment group (Placebo, ZX008 0.2 mg/kg/day ZX008 0.8 mg/kg/day).

Continuous data will be summarized using descriptive statistics including means, standard deviations, medians, lower and upper quartiles, minimum and maximum values. Categorical variables will be summarized with frequencies and percentages. Confidence intervals will be calculated for key parameters or estimates as warranted.

Two-sided statistical significance testing (α = 0.05) comparing each active treatment to placebo will be performed for the primary and secondary endpoints as described below, unless otherwise noted.

All relevant collected subject data will be included in listings. All subjects entered into the database will be included in data listings.

Unless otherwise specified in the subsequent sections, in the event of multiple assessments at a given planned time point, the latest collected value will be used for the summarization.

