8.2.2. Part 1 Primary Efficacy Endpoint Analyses

T+M Period:

The primary analysis will compare the ZX008 0.8 mg/kg/day group to the placebo group for Cohort A using a two-sided test at the α =0.05 level of significance.

The primary endpoint will be analyzed using a non-parametric analysis of covariance (ANCOVA) model with treatment group (three levels; Placebo, 0.2 mg/kg/day, 0.8 mg/kg/day) and weight strata group (< 37.5 kg, \geq 37.5 kg) as factors, rank of baseline DSF_B as a covariate and rank of percent CDSF_{T+M} as response. Treatment group mean differences from placebo will be estimated via least squares means from the analysis model along with 95% confidence intervals.

The null hypothesis

$$H_0$$
: $\mu_{Z0.8} - \mu_P = 0$,

will be tested against the alternative

$$H_A$$
: $\mu_{Z0.8} - \mu_P \neq 0$,

where $\mu_{Z0.8}$ and μ_P represent the ZX008 0.8 mg/kg and Placebo group location parameter, respectively.

Rejection of the null hypothesis in favor of the alternative, in the presence of a statistically significantly smaller seizure frequency for the treatment group compared to the placebo group, (two-sided p-value <.05) will be regarded as evidence of a treatment benefit in favor of the 0.8 mg/kg group. A similar comparison of the location parameter for Z008 0.2 mg/kg/day vs. placebo will be regarded as evidence of a treatment benefit of the 0.2 mg/kg group. This is the 3rd key secondary endpoint.

Sample SAS code for the non-parametric ANCOVA described above is as follows:

```
Proc rank data=temp ties=mean out=ranktemp;
Var bsrd csrd;
Rank r_bsrd r_csrd;
Run;
proc glm data=ranktemp;
    class wtgrp trtp;
    model r_csrd = r_bsrd wtgrp trtp / SS3;
    lsmeans trtp / pdiff stderr;
```

where trtp = randomized treatment group (with codes 1, 2, 3 indicating placebo, 0.2 mg/kg, and 0.8 mg/kg groups).

```
r_bsrd = rank of baseline DSF_B,
r_csrd = rank of percent CDSF_{T+M}
wtgrp = weight group.
```

Additional statements may be used to obtain estimates and associated 95% confidence intervals.

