8.4.7. Rescue Medication Usage

Use of rescue medication is recorded on the daily diary. In the event of prolonged seizures or status epilepticus, rescue medication is administered according to each subject's personalized regimen consisting of one or more medications. If the first rescue administration does not control the seizures, a second or even third round might be administered. They second and third round might use different medications or different doses than the first round of rescue meds.

Rescue medication will be summarized by treatment group and comparisons of active treatment vs. Placebo for the following:

• The number of days rescue medication was taken (normalized to 28 days) will be summarized separately for the Baseline and T+M periods by the mean (SD) as well as the median, minimum and maximum values. Multiple medications taken on the same day will be counted once for that day. The ZX008 group will be compared to the placebo group using a non-parametric ANCOVA analogous to that described in the primary efficacy endpoint section. Specifically, the rank ANCOVA will use the ranks of rescue medication frequency during T+M or M period as the response, and will incorporate treatment group as a factor and the ranks of rescue medication frequency during Baseline as a covariate.

The number of medications used per episode will be summarized using similar descriptive statistics as above. Rescue medications related to an episode of SE are considered to be all rescue administered on the day of the SE (or seizure lasting >10 min). If more than one episode of SE or a seizure lasting >10 min occurred in a single day, the rescue medication for that episode is all rescue administered after the seizure until the start time of the next prolonged seizure.

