Section 2 (USA Version) or	Quality of Life Item	2.1 or 9.1
Section 9 (Australia Version):		
Quality of Life		
Overall Quality of Life *		Average of 16 subscale scores*

^{*}An Overall Quality of Life Score will be computed by adding each subscale score for each individual and then dividing by 16.

[figure not shown]
For each treatment group and at each schedule visit, the descriptive statistics will be presented for each QOLCE subscale and for the overall quality of life score.

[figure not shown]
In addition, the change from baseline in the overall QOLCE will be calculated for each subject by subtracting the Part 1 baseline score from the score measured at each scheduled post-baseline visit. The change from baseline for each treatment group will be summarized by summary statistics. Treatment groups will be compared using pairwise Wilcoxon Rank-sum tests.

Individual subject data for the domains will be listed.

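### SAP 8.4.4 tests the longest drop-free interval with an unadjusted Wilcoxon test: valid, but less powerful than the rank ANCOVA the SAP already uses elsewhere

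*SAP*

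**What the plan says.** SAP 8.4.4 derives, for each subject, the longest run of days between ESC-confirmed drop seizures over titration plus maintenance. For inference it says: "The Wilcoxon rank sum test will be used to test for differences between each treatment arm and placebo". The effect size is a Hodges-Lehmann interval for the difference between groups. No covariate or stratum is named.

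Other efficacy sections are handled differently:

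- Primary endpoint (8.2.2): a rank ANCOVA with treatment and weight stratum as factors, and "rank of baseline DSF_B as a covariate and rank of percent CDSF_{T+M} as response".
- Seizure-free days (8.4.3), taken from the same diary: the comparison "using the baseline as covariate will be done with a similar non-parametric ANCOVA model as described for the primary analysis".
- Design (section 4): "Randomization is stratified by weight", with a cut at 37.5 kg.

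Section 5.3 lists the longest interval as an additional secondary endpoint. Section 8.1 limits error control to the primary and key secondary objectives. Section 6.6.1 nevertheless provides for "Two-sided statistical significance testing (α = 0.05) comparing each active treatment to placebo" on the secondary endpoints, so a p-value for this one will be reported.

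**The concern.** How long a subject can go without a drop seizure depends heavily on how often that subject has them. The longest interval is not a change from baseline, so nothing in the 8.4.4 analysis removes between-subject differences in seizure rate. They stay in the comparison as noise. Baseline drop seizure frequency is already derived for every subject for the primary analysis, so the information is available and unused.

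Two things are at stake: power, and comparability with the adjacent endpoint. The longest interval could look null beside a positive seizure-free-days result partly because one test is adjusted and the other is not.

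**Working it through.** **1. The plan's own figures.** The SAP gives no power, effect size or baseline correlation for this endpoint. Its sample size in 4.2 is for the primary endpoint: 30 points, SD 50%, 90% power, two-sided 0.05. A t-test needs 60 per group; 60/0.955 = 62.8, so 63; 63/0.8 = 78.75, so 79; 3 × 79 = 237. These reproduce. (The text's 14 additional subjects per group should be 79 − 63 = 16; the totals are unaffected.) Only two inputs are borrowed here: 79 per arm, and the example of a 10% against a 40% decrease.

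**2. Analytic check.** Let ρ be the rank correlation between baseline frequency and longest interval. The unadjusted test's noncentrality is approximately the adjusted test's multiplied by √(1 − ρ²). For adjusted power of 80% the noncentrality is 1.960 + 0.842 = 2.802. With ρ = 0.7 this gives 2.802 × 0.714 = 2.001, and power Φ(2.001 − 1.960) = 0.516. The share lost is 1 − 0.516/0.80 = 36%.

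| ρ (absolute) | Unadjusted power if adjusted = 80% | Share lost | Unadjusted power if adjusted = 90% | Share lost |
|---|---|---|---|---|
| 0.3 | 76% | 5% | 87% | 3% |
| 0.5 | 68% | 15% | 80% | 11% |
| 0.6 | 61% | 24% | 74% | 18% |
| 0.7 | 52% | 36% | 64% | 29% |
| 0.8 | 39% | 51% | 49% | 45% |

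**3. Simulation.** Settings: 79 per arm, 98 days of treatment, overdispersed daily counts, interval derived as in 8.4.4, no dropout, weight stratum not prognostic. The baseline distributions are assumptions; the SAP gives none.

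- **A.** SAP example, rates 0.90 and 0.60 of baseline. Median 20-75 drop seizures per 28 days, between-subject log-SD 0.8 or 1.1, subject-response log-SD 0.5 or 0.8; 12 scenarios of 500 trials.
- **B.** Active rate 30% below placebo, close to the 1 − 0.60/0.90 = 33% implied by the SAP example. Median 20, 50 or 80, between-subject log-SD 0.8 or 1.2, within-subject change log-SD 0.4, 0.7 or 1.0; 18 scenarios of 400 trials.
- **C.** Active rate 50% below placebo, median 50; 4 scenarios of 500 trials.

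| Set | Wilcoxon | Rank ANCOVA | Share of power lost | Baseline rank correlation |
|---|---|---|---|---|
| A | 39-65% | 62-86% | 22-48% | −0.54 to −0.76 |
| B | 25-58% | 40-85% | 20-56% | −0.49 to −0.81 |
| C | 69-94% | 92-100% | 6-25% | −0.58 to −0.81 |

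In set A the absolute loss was 15-38 percentage points. A separate run at the set A effect (300 trials per setting) had Wilcoxon keeping 48-79% of the adjusted power, a loss of 21-52%. The same run with rates 0.90 and 0.50 of baseline kept 73-93%.

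One setting shows how the loss depends on effect size (median 50, log-SD 1.2, change log-SD 0.7). At a 30% reduction power was 0.34 against 0.60, a loss of 43%. At a 50% reduction it was 0.83 against 0.99, a loss of 16%.

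**4. Validity.** With no treatment effect, the Wilcoxon test rejected in 4-6% of trials.

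**The case against.** The case for leaving 8.4.4 alone has four parts.

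*The size is not a property of this plan.* The SAP supplies no baseline distribution or correlation, and the loss moves with both. This stands. A reader might infer that the test throws away about half the power. The documents do not support that as a general statement: one half is the pessimistic end, reached analytically only near ρ = 0.8.

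*The test is valid and nothing confirmatory depends on it.* This also stands. A reader might infer that chance baseline imbalance distorts the p-value. It does not: under randomisation the null distribution already allows for it, and the simulated type I error is close to nominal. What is lost is precision.

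*Wilcoxon and Hodges-Lehmann form a matched pair.* An adjusted p-value beside an unadjusted interval in days may not agree exactly. That is a genuine but small cost. Nor does the longest run over 14 weeks have a same-scale baseline, since a 28-day baseline caps it. Baseline frequency can still serve as the covariate, so this does not block adjustment.

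*Other sections look similar.* A reader might extend the point to QOLCE (8.4.10), where "Treatment groups will be compared using pairwise Wilcoxon Rank-sum tests", and to rescue medication (8.4.7), whose model "will incorporate treatment group as a factor and the ranks of rescue medication frequency during Baseline as a covariate". Neither is the same defect. QOLCE tests change from baseline, so baseline already enters, and it is exploratory. Rescue-medication days, also exploratory, are already baseline-adjusted; only the weight stratum goes unnamed. No gain from the stratum was shown, because it was simulated as non-prognostic.

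**Conclusion.** The point holds as one of efficiency and consistency for 8.4.4 alone. The unadjusted Wilcoxon test is valid, but it leaves out a strong predictor that the SAP uses for the primary endpoint and for seizure-free days. Under the SAP's planning example with 79 per arm, and the assumed baseline distributions (median about 20-75 drop seizures per 28 days, between-subject log-SD 0.8-1.1, no dropout), it gives away roughly 20-50% of the adjusted test's power. The loss is smaller if the effect is larger or the baseline correlation lower: about 5% at ρ = 0.3 when adjusted power is 80%. All the gain shown comes from baseline frequency. The trial's primary and key secondary conclusions are unaffected. The change is worth making because it costs almost nothing.

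**What to change.** In 8.4.4, make the 8.2.2 rank ANCOVA the test: rank of the longest interval as response, treatment (three levels) and weight stratum as factors, rank of baseline drop seizure frequency as covariate. Keep the Wilcoxon test with its Hodges-Lehmann interval as a supportive analysis, labelled unadjusted, and note that the interval may not agree exactly with the adjusted p-value.

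Optionally, and for consistency only, name the weight stratum in the 8.4.7 rescue-medication model. QOLCE needs no change on this account.

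The cost is a few lines of SAP text and reuse of the 8.2.2 code, with no new data. The 2021 SAP addendum indicates that the Cohort A analyses are complete, so an adjusted test there would have to be labelled post hoc.
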